### **7.2.5. Time to Treatment Failure (TTF)**

TTF is the time from the first dose of study drug to treatment failure (any treatment discontinuation due to PD, toxicity, or death). The analysis of TTF will be performed based on the assessment by IRRC and investigator, separately.

TTF will be summarized using Kaplan-Meier summary statistics for PEP FL and ITT MZL population. The median TTF with 95% CIs (Brookmeyer and Crowley method), number of events, number censored, and KM plot of proportion of subjects without treatment failure over time will be presented. TTF will be reported in months. Estimate and 95% CI for 1-year TTF rate, and reverse KM estimate median with 95% CI for follow-up time (months) will be summarized.

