### **7.2.2. Duration of Response (DOR) and Duration of Recaptured Response (DORR)**

Duration of response (DOR) will be evaluated as a secondary endpoint and is defined as the time from documentation of the first CR or PR to the time of first disease progression based on the Modified Lugano Response Criteria. The endpoint DOR will be assessed by the IRRC and Investigator independently. To evaluate the duration of response for subjects who had recapture of response ([Section 7.2.5](#)) on the CS dosing, duration of recaptured response (DORR) is defined as the time from recapture of response to the time of second disease progression. The endpoint DORR will be assessed by the Investigator only.

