### 11.2.2. Statistical Analyses

The primary analysis of ORR for FL will be triggered after all 91 subjects in the PEP enrolled in the study (except those who discontinue early) have been followed for at least 6 months from the start of study drug.

The final analysis of DOR for FL will be triggered after most responders in the Primary Efficacy Population have a minimum of 12 months of follow-up from first response.

The final analysis of ORR and DOR for MZL will be triggered after most of the responders in the MZL ITT population (except those who discontinue early) have been followed for at least 12 months from first response.

Summary statistics for continuous variables will include the mean, standard deviation, median, and range (minimum/maximum). Categorical variables will be presented as frequency counts and percentages. Time-to-event variables will be summarized using Kaplan-Meier (KM) methods (median, 95% CI, number of events, number censored, KM figures). Data listings will be created to support each table and to present all data.

The efficacy analysis of ORR for MZL as determined by the IRRC will be based on the ITT MZL Population, utilizing the best overall ORR prior to first PD. The CR rate as determined by the IRRC will be reported similarly. The ORR as determined by the IRRC in the EE Population will be reported as a sensitivity analysis.

Secondary efficacy endpoints including DOR, DORR, PFS, TTF, time to recapture of response (as assessed by the IRRC and/or Investigator); and overall survival (OS) will be summarized using KM summary statistics for the ITT IS FL Population and ITT MZL Population respectively.

Similarly, the efficacy endpoints based on Investigator assessments will be summarized as supportive analyses.

Safety analyses will be performed on the Safety Population, as defined in [Section 11.2.1](#).

Overall summary of safety will include but not limited to the following analyses:

- TEAEs, including severity and possible relationship to study drug and/or study treatment
- AESIs
- treatment-emergent SAEs
- discontinuations from study treatment due to AEs
- treatment-emergent abnormal changes in laboratory values
- treatment-emergent abnormal changes in vital signs.

The rate of AESIs and the respective 95% CI will be calculated by dosing group (CS and IS) and overall.

Time to AESIs will be calculated from the first day of study treatment to first occurrence of AESI, utilizing KM methodology.

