##### **3.2.2. Duration of Response (DOR) and Duration of Recaptured Response (DORR)**

DOR is defined as time from first (CR or PR) response to the time of first PD (based on the Modified Lugano Response Criteria) or the date of death due to any cause (whichever occurs earlier).

For Primary Analysis and NDA Analysis for FL, DOR will be analyzed based on the patients who achieved PR or CR prior to first PD, that is reported before the data cutoff date for the FL Primary Analysis.

As a supportive analysis for NDA Analysis for FL, DOR will be analyzed based on all patients who achieved PR or CR prior to first PD, that is reported before the data cutoff date for the NDA Analysis for FL submission.

To evaluate the duration of response for subjects who had recapture of response on the CS dosing ([Section 3.2.6](#)), DORR is defined as the time from recapture of response (CR or PR) to the time of second PD or the date of death due to any cause (whichever occurs earlier).

Detailed censoring rules are specified in [Table 2](#) (FDA guidance [[FDA 2015](#)] and [[FDA 2018](#)]). In general, in primary analysis for DOR and analysis for DORR, subjects will be censored at the date of last adequate assessment with evidence of no progression by the IRRC, in the following situations:

- No progression nor death
- Discontinuation for any reason other than IRRC documented PD or death, including loss to follow-up, toxicity, withdrawal of consent, etc.
- Start of new anti-lymphoma treatment without evidence of IRRC documented PD
- Death or progression after two or more consecutive missed scheduled visits.

Supportive analysis for DOR will be conducted to evaluate the robustness of the primary analysis result for DOR, by considering all progressions and deaths as events per European Medicines Agency (EMA) guidance ([EMA 2013](#)), regardless of whether they occurred after initiating next anti-lymphoma treatment, after 2 or more consecutive missed scheduled assessments, or being reported as clinical (non-IRRC reviewed radiographic) progression ([Table 3](#)).

For subjects in IS dosing switching to the CS at PD, both DOR and DORR will be estimated.

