### **7.2.6. Recapture of Response Rate (RRR)**

RRR is the proportion of subjects who achieved a CR or PR followed by a PD during IS dosing and subsequently switched to CS dosing and achieved a second documented CR or PR. The analysis of RRR will be performed based on the assessment by IRRC and investigator, separately.

For RRR, the number and percent (%) of subjects with 2-sided 95% exact Clopper-Pearson CIs will be summarized for subjects who achieved a CR or PR followed by a PD during IS dosing and subsequently switched to CS dosing, in PEP FL and ITT MZL population.

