#### **7.2.7. Time to Recapture of Response**

Time to recapture of response is the time from the first PD until the second documented CR or PR. The analysis of time to recapture of response will be performed based on the assessment by IRRC and investigator, separately.

Time to recapture of response will be summarized using Kaplan-Meier summary statistics only for subjects who achieved a CR or PR followed by a PD during IS dosing and subsequently switched to the CS dosing, in PEP FL and ITT MZL population. The median time to recapture of response with 95% CI (Brookmeyer and Crowley method), number of events, number censored and, and KM plot of proportion of subjects without recapture of response over time will be presented. Time to recapture of response will be reported in months. Estimate and 95% CI for 1-year rate of time to recapture of response, and reverse KM estimate median with 95% CI for follow-up time (months) will be summarized.

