## **10. CHANGES FROM ANALYSIS PLANNED IN PROTOCOL**

No changes from planned analysis in protocol.

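### For FL, the SAP summarizes TTF and time to recapture in the 91-subject PEP only, where the protocol names the wider ITT IS FL Population; the two documents also define DOR and DORR differently

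*SAP*

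**What the plan says.** Protocol 11.2.2 opens its list with "Secondary efficacy endpoints including DOR, DORR, PFS, TTF, time to recapture of response (as assessed by the IRRC and/or Investigator", adds OS, and says that these "will be summarized using KM summary statistics for the ITT IS FL Population and ITT MZL Population respectively". The ITT IS FL Population is every FL subject intended for the intermittent schedule. The PEP is the first 91 consecutive subjects in it (Protocol 11.2.1, SAP 4.3).

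The SAP is narrower for some of these endpoints:

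- TTF (7.2.5): "TTF will be summarized using Kaplan-Meier summary statistics for PEP FL and ITT MZL population".
- Time to recapture (7.2.7): responders who progressed on the intermittent schedule and "subsequently switched to the CS dosing, in PEP FL and ITT MZL population".
- Recapture rate (7.2.6): the same kind of subject, "subsequently switched to CS dosing, in PEP FL and ITT MZL population".
- SAP Table 4 places all secondary endpoints on PEP FL at the NDA Analysis for FL.

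On definitions, Protocol 7.2.2 gives DOR as "the time from documentation of the first CR or PR to the time of first disease progression" and ends DORR at second progression. SAP 3.2.2 ends both at progression "or the date of death due to any cause (whichever occurs earlier". SAP 7.2.2 repeats this, and SAP Table 2 codes death as an event.

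SAP Section 10 reads "No changes from planned analysis in protocol".

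**The concern.** A programmer who follows SAP 7.2.5 and 7.2.7 would not produce the TTF and time-to-recapture analyses that the protocol describes. Neither document says why these descriptive endpoints should be confined to the set sized for the ORR test. The loss matters most for recapture. That analysis counts only subjects who responded, progressed, switched to continuous dosing and were then reassessed, so it will rest on few people.

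The definition mismatch is a separate matter. If death is not an event for DOR, a responder who dies without progression does not end a response. Two readers working from the two documents could therefore report different medians under the same endpoint name. Protocol 7.2.3 does name death from any cause for PFS, so its absence from DOR is noticeable.

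**Working it through.** **What the 91 is.** Inputs (Protocol 11.1, SAP 2.4): null ORR 48%, alternative 65.5%, one-sided alpha 0.025, power at least 90%. In an exact binomial test with n = 91, the smallest r with P(X ≥ r | 0.48) ≤ 0.025 is 54. The exact size is 0.0196 and the power at 65.5% is 0.910. The plan's figure reproduces, so the PEP is the ORR sizing set.

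**FL populations side by side.**

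| Endpoint | Protocol 11.2.2 | SAP Section 7.2 | SAP Table 4, NDA Analysis |
|---|---|---|---|
| TTF | ITT IS FL | PEP FL (7.2.5) | PEP FL |
| Time to recapture | ITT IS FL | PEP FL (7.2.7) | PEP FL |
| DORR | ITT IS FL | none named (7.2.2) | PEP FL |
| Recapture rate | none named | PEP FL (7.2.6) | PEP FL |
| PFS, OS | ITT IS FL | PEP FL plus ITT FL (7.2.4, 7.2.8) | PEP FL, with a further row that has an ITT IS FL column |

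SAP 7.2.3 also adds ITT FL for CR rate. The SAP authors therefore added a wider set where they wanted one, and 7.2.5 to 7.2.7 lack it. SAP 4.2 nevertheless says in general terms that ITT FL serves the efficacy endpoints.

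**Subjects left out.** Protocol 8.3 gives 121 FL subjects enrolled and treated on the intermittent schedule.

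- 121 − 91 = 30, and 30/121 = 24.8%.
- With the planned 120 instead: 29/120 = 24.2%.

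**Largest possible gain in precision.** If every added subject carried the same information as a PEP subject, interval width would scale by sqrt(91/121) = 0.867, a narrowing of about 13%. With no censoring, the 95% half-width is 1.96 × sqrt(p(1 − p)/n):

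| Assumed 1-year TTF rate | n = 91 | n = 121 |
|---|---|---|
| 50% | ±10.3 points | ±8.9 points |
| 80% | ±8.2 points | ±7.1 points |

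These are upper bounds on the gain, because the added subjects enrolled last.

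**How far the DOR definitions could diverge.** The documents do not give the share d of first events that are deaths, so d is assumed over a range. With independent exponential hazards, the progression-only median divided by the progression-or-death median is 1/(1 − d).

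| d | Ratio of medians |
|---|---|
| 2% | 1.02 |
| 5% | 1.05 |
| 10% | 1.11 |
| 20% | 1.25 |

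This measures the gap between the two written definitions. It is not a bias in the planned analysis, which uses the SAP rule.

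**The case against.** The best case for the SAP is that the PEP is a reasonable set for Kaplan-Meier endpoints at that cutoff. The NDA Analysis is triggered by 12 months of follow-up in most PEP responders, so follow-up is assured there and not in the later subjects. This stands as a reason to keep the PEP analysis. It does not explain dropping the population that the protocol names.

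Table 4 also leaves some room. Its row for selected critical efficacy endpoints names PFS and OS and ends in etc., and ITT IS FL columns appear for baseline, supportive ORR and supportive DOR as well. With SAP 4.2, this makes the SAP ambiguous; it is not a plain decision to exclude subjects. The endpoint-specific sections are still what would be programmed.

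Four stronger readings are tempting, and the documents do not support them:

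- *SAP Section 10 was false when signed.* SAP v3.0 was updated to Protocol Amendment 4, and the protocol in hand formalizes changes in Amendment 5. The Amendment 4 text is not available, so only a conflict between the current documents can be shown.
- *The recapture rate contradicts the protocol.* Protocol 11.2.2 names time to recapture and DORR, and neither it nor Protocol 7.2.5 gives a population for the rate.
- *DOR will be overstated.* The SAP counts deaths, and the protocol is silent on death for DOR; it does not say that deaths are censored.
- *The primary DOR population is wrong.* Protocol 11.2.1 itself defines a PEP-based DOR Primary Analysis Set.

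**Conclusion.** The population conflict is real for TTF and time to recapture. It extends to DORR through Table 4, since SAP 7.2.2 names no FL population for DORR. About 30 of 121 subjects (25%) are left out. The figure of 121 counts subjects enrolled and treated, whereas ITT IS FL is defined by randomization, re-consent date or enrollment, so its exact size is not given and may differ slightly. The 13% narrowing is a ceiling that assumes equal information per subject. A proportional rise in potential switchers (30/91, about a third) is likewise a ceiling, because recapture takes time to occur and the added subjects have had less of it.

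The DOR and DORR definitions differ between the documents. The SAP rule, with death as an event, is the sound one and governs what will be run, so this part is an alignment of protocol wording.

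Both matters concern descriptive secondary endpoints. The primary ORR test in the PEP is untouched. The change is worth making, but the trial's main conclusion does not depend on it.

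**What to change.** 1. In SAP 7.2.5 (TTF), 7.2.7 (time to recapture), 7.2.2 (for DORR) and Table 4, add ITT IS FL at the NDA Analysis beside PEP FL. Do the same for the recapture rate in 7.2.6 for consistency, although the protocol names no population for it.
2. In Protocol 7.2.2, extend the DOR and DORR definitions so that each ends at progression or death from any cause, whichever comes first.
3. When the SAP is brought from Amendment 4 to Amendment 5, replace the statement in SAP Section 10 with a list of any differences that remain.

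The cost is wording in two documents and a few extra table columns, with no new data collection. The added columns will include subjects with shorter follow-up. A footnote should say so, and the reverse Kaplan-Meier follow-up already planned for TTF, time to recapture and DORR should be shown for each population.

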### **7.2.6. Recapture of Response Rate (RRR)**

RRR is the proportion of subjects who achieved a CR or PR followed by a PD during IS dosing and subsequently switched to CS dosing and achieved a second documented CR or PR. The analysis of RRR will be performed based on the assessment by IRRC and investigator, separately.

For RRR, the number and percent (%) of subjects with 2-sided 95% exact Clopper-Pearson CIs will be summarized for subjects who achieved a CR or PR followed by a PD during IS dosing and subsequently switched to CS dosing, in PEP FL and ITT MZL population.

#### **7.2.7. Time to Recapture of Response**

Time to recapture of response is the time from the first PD until the second documented CR or PR. The analysis of time to recapture of response will be performed based on the assessment by IRRC and investigator, separately.

Time to recapture of response will be summarized using Kaplan-Meier summary statistics only for subjects who achieved a CR or PR followed by a PD during IS dosing and subsequently switched to the CS dosing, in PEP FL and ITT MZL population. The median time to recapture of response with 95% CI (Brookmeyer and Crowley method), number of events, number censored and, and KM plot of proportion of subjects without recapture of response over time will be presented. Time to recapture of response will be reported in months. Estimate and 95% CI for 1-year rate of time to recapture of response, and reverse KM estimate median with 95% CI for follow-up time (months) will be summarized.

#### **7.2.8. Overall Survival (OS)**

OS is the time from date of first dose of study drug until death from any cause, and will be summarized by Kaplan-Meier summary statistics for PEP-FL, ITT MZL population, ITT FL population (for NDA Analysis for FL only).

Kaplan-Meier plots of OS will be presented. Summaries of the number and percentage of subjects who had died, were still in survival follow-up, were lost to follow-up and had withdrawn consent will be provided along with the median OS times and 95% CIs (Brookmeyer and Crowley method). Overall survival will be reported in months. Estimate and 95% CI for 1-year OS rate, and reverse KM estimate median with 95% CI for follow-up time (months) will be summarized.

## **8. SAFETY ANALYSES**

Safety analyses will be presented and summarized in the safety population for the Primary Analysis for FL and NDA Analysis for FL, and include overall IS group, IS FL, MZL, and CS group.

Safety IS FL population will be used to analyze safety endpoints for the FL Primary Analysis.

### **8.1. Extent of Exposure**

Exposure to ME-401 will be evaluated by duration of study drug exposure (months), actual dose intensity, and relative dose intensity for the safety population.

Descriptive statistics will be presented for continuous exposure variables: duration of exposure, actual dose intensity, and relative dose intensity. The number and percentage of subjects with dose schedule modified or dose interrupted due to AE or progressive disease will be summarized. The number and percentage of subjects with dose missed will be summarized by

reason. For subjects on study drug at the time of the ORR analysis, the data cut-off (DCO) date will be used to calculate exposure.

- Duration of exposure (months) = (Date of last non-zero dose – Date of first non-zero dose +1) /30.4375.
- Duration of exposure on the CS (months)
  - = (Date of last non-zero CS dose – Date of first non-zero CS dose +1) /30.4375 for subjects who never switched dosing regimen; or
  - = sum of (Date of last non-zero CS dose – Date of first non-zero CS dose +1) /30.4375 from each CS dosing interval for subjects who switched dosing regimens; date of first or last CS dose can be derived based on the switching date.
- Duration of exposure on the IS (months)
  - = (Date of last zero/non-zero IS dose – Date of first non-zero IS dose +1) /30.4375
- Actual total dose exposed (mg) is defined as the sum of ‘total mg’ of study drug received.
- Total dose intended (mg) is defined as the sum of ‘total mg’ of study drug planned.
  - Total dose intended for the CS is estimated to be 60 mg x Duration of exposure on the CS (months) x 30.4375
  - Total dose intended for the IS is estimated to be (60 mg /4) x Duration of exposure on the IS (months) x 30.4375
- Actual dose intensity (mg/month) = 30.4375 x Actual total dose exposed (mg) ÷ [(Date of last dose, zero or non-zero dose of study drug) – (Date of first non-zero dose of study drug) + 1]
- Intended dose intensity (mg/month) = 30.4375 x Total dose intended (mg) ÷ [(Date of last dose, zero or non-zero dose of study drug) – (Date of first non-zero dose of study drug) + 1]
- Relative dose intensity (RDI) (%) is the percentage of the actual dose intensity delivered relative to the intended dose intensity through to study drug discontinuation. RDI (%) = (actual dose intensity) ÷ (intended dose intensity) x 100

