## 2.3. Brief Description

Under Protocol Amendment 2, this is a global, multicenter, open label, single-arm, phase 2 study of the PI3K $\delta$  inhibitor ME-401 (zandelisib) in subjects with relapsed/refractory FL or MZL. ME-401 will be administered orally at a dose of 60 mg given once a day in 28-day cycles, with the first day of treatment designated as Day 1. Treatment with ME-401 can be administered based on a continuous schedule (CS) or an intermittent schedule (IS).

[figure not shown]
The CS (or Group A in Protocol Amendment 1) includes daily dosing for the whole duration of a treatment cycle until protocol-defined criteria is met for treatment interruption, modification to intermittent dosing to manage toxicity, or discontinuation.

The IS (or Group B in Protocol Amendment 1) includes:

- continuous daily therapy for the initial 2 cycles (~56 days) of treatment
- the intermittent treatment begins at Cycle 3, with ME-401 administered daily for the first 7 days of every 28-day cycle (7 days on treatment and 21 days off treatment)

Under Protocol Amendment 1 (Figure 1a), subjects were randomized 1:1 to receive CS or IS. Since Protocol Amendment 2 (Figure 1b), the initial CS treatment arm was terminated, and all new subjects were enrolled to receive therapy on the IS only. If CS subjects already completed 2 initial cycles of therapy, they were switched to IS dosing after they complete therapy in the ongoing cycle of treatment, and if they had not completed the first 2 cycles of therapy they were switched to IS dosing after completion of the first two cycles of therapy on CS. Subjects who progress on IS dosing may be switched to CS dosing. Subjects will continue to receive study drug in accordance with the IS dosing regimen (or CS dosing regimen if switched from IS after disease progression [PD]) until investigator-assessed disease progression or unmanageable toxicity requiring treatment discontinuation, subject's decision to withdraw their consent to participate on study, or study closure by the Sponsor.

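### SAP 8.1 ends total exposure and IS exposure on different dates, and sums CS but not IS intervals, so total and component durations do not reconcile

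*SAP*

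**What the plan says.** All the definitions at issue are in SAP Section 8.1.

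- **Total duration** is "Duration of exposure (months) = (Date of last non-zero dose" minus the date of the first non-zero dose, plus one day, in months of 30.4375 days.
- **IS duration** starts at the first non-zero IS dose but ends at the "Date of last zero/non-zero IS dose". It is a single span.
- **CS duration** ends at a non-zero CS dose and is summed "from each CS dosing interval for subjects who switched dosing regimens".
- **Actual and intended dose intensity** share a denominator that ends at the last dose of study drug, zero or non-zero.
- **Intended dose** is 60 mg per day of CS duration plus 60/4 = 15 mg per day of IS duration. Section 8.2 divides dose received by this quantity to get compliance.
- **Ongoing subjects:** "For subjects on study drug at the time of the ORR analysis, the data cut-off (DCO) date will be used to calculate exposure".

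SAP Section 2.3 describes the IS as "continuous daily therapy for the initial 2 cycles (~56 days) of treatment" and then, from Cycle 3, "with ME-401 administered daily for the first 7 days of every 28-day cycle (7 days on treatment and 21 days off treatment". Section 8.1 does not say whether those first 56 days belong to IS or CS duration.

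**The concern.** From Cycle 3 each IS cycle ends with 21 planned drug-free days. Total duration drops the last such period for a subject who has stopped. IS duration keeps it, and so does the cut-off rule for a subject still on treatment. Two subjects with the same dosing history can then have different total exposure only because one had discontinued by the cut-off.

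The second problem is independent of the first. Where CS dosing falls between two IS periods, the single IS span runs across it, and the CS sum counts it again. Because intended IS dose is proportional to IS duration, the double count passes into compliance and RDI.

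Duration of exposure is the first exposure variable named in Section 8.1, and the case for the IS in Protocol Section 2.3 rests on long-term tolerability. These figures should agree with each other.

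**Working it through.** The plan states no exposure figure to reproduce, so the formulas are applied to constructed dosing records.

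**Inputs.** From SAP 2.3: 60 mg daily on Days 1–56, then 7 days on and 21 off. From SAP 8.1: the definitions above. Assumption: off days are recorded as zero doses, as the wording of the IS end date implies.

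**1. End dates.** A subject stops at the end of Cycle n, with n at least 3.

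- Total = 28(n − 1) + 7 days, because the last non-zero dose is on day 7 of Cycle n.
- IS, with the lead-in counted as IS = 28n days.
- With the lead-in counted as CS: CS = 56, IS = 28n − 56, sum = 28n days.

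| Stops at end of cycle | Total, days (months) | IS, lead-in as IS | IS, lead-in as CS | IS + CS, either reading |
|---|---|---|---|---|
| 3 | 63 (2.07) | 84 | 28 | 84 (2.76) |
| 6 | 147 (4.83) | 168 | 112 | 168 (5.52) |
| 13 | 343 (11.27) | 364 | 308 | 364 (11.96) |

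The gap between total and IS + CS is 21 days, 21/30.4375 = 0.69 months, at every n. As a share of the 28n-day course it is 21/84 = 25%, 21/168 = 12.5% and 21/364 = 5.8%. A subject with the Cycle 6 course who is still on drug at a Day 168 cut-off has a total of 168 days instead of 147.

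RDI is actual divided by intended dose intensity. Both use the same denominator, which cancels, and total duration does not enter the intended dose. The end-date mismatch therefore leaves RDI unchanged.

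**2. IS intervals not summed.** The sequence is permitted. SAP 2.3 allows a switch from IS to CS after progression. Protocol Section 5.3.1 resumes treatment on the IS after a toxicity interruption. Illustrative record, with no hold between schedules: IS Days 1–252, CS Days 253–336, IS Days 337–420, all doses taken.

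With the lead-in counted as CS:

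- CS = 56 + 84 = 140 days; intended and received 140 × 60 = 8,400 mg.
- IS as a span, Days 57–420 = 364 days; intended 364 × 15 = 5,460 mg.
- IS as a sum, (252 − 56) + 84 = 280 days; intended 280 × 15 = 4,200 mg.
- IS received: 10 cycles × 7 days × 60 mg = 4,200 mg.
- Excess intended dose: 84 × 15 = 1,260 mg.
- IS compliance: 4,200/5,460 = 77%, against 100% if summed.
- Overall compliance and RDI: (8,400 + 4,200)/(8,400 + 5,460) = 12,600/13,860 = 91%, against 100% if summed.
- IS + CS = 364 + 140 = 504 days in a 420-day course. The SAP's own total is 399 days, the last non-zero dose being on Day 399.

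With the lead-in counted as IS, the span is 420 days and CS is 84, again 504, and the excess intended dose is again 1,260 mg. The compliance percentages do not carry over. On that reading the 15 mg rate already misstates the lead-in: a fully compliant six-cycle subject has RDI 5,040/2,520 = 200%, against 5,040/5,040 = 100% with the lead-in as CS.

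**The case against.** Ending total duration at the last dose taken is an explicit and defensible definition. The zero-dose end date for the IS looks deliberate, because a rate of 60 mg/4 makes sense only if off days are counted. The SAP never says that IS and CS durations must add to the total. The main schedule changes it describes (CS to IS under Amendment 2, IS to CS after progression) give at most two CS intervals and one IS interval, which would explain why only CS is summed. All of this is fair. It does not explain why total duration differs from the dose-intensity denominators in the same section, or why stopped and ongoing subjects are measured differently.

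Several stronger readings are tempting but not supported:

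- **That not summing IS intervals makes IS exceed total.** It does not. Once both end on the same kind of dose, the IS span lies within the total span. The effect is that IS + CS exceeds total.
- **That IS alone always exceeds total after a completed off period.** In the cases tabulated, this needs the lead-in to count as IS. SAP 2.3 describes it that way, but the 15 mg rate fits only if it counts as CS. On the second reading IS is 112 days against a total of 147 at Cycle 6, and only the sum exceeds the total.
- **That contradictory durations will appear in one table.** Section 8.1 lists total duration and the two dose intensities for summary. It does not say where, or whether, the component durations are tabulated.

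**Conclusion.** Both inconsistencies stand as separate points. The first omits up to 21 planned off days (0.69 months) from total exposure for a discontinued IS subject, relative to an ongoing subject with the same course. It holds under either treatment of the lead-in, since IS + CS exceeds total both ways. It depends on off days being recorded as zero doses. A subject who stops within the seven dosing days with no later zero-dose record has no gap, and stopping partway through an off period gives a smaller one.

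The second arises only in IS-CS-IS subjects, whose number the documents do not give. For each of them, intended IS dose is too high by 15 mg per intervening CS day. The 77% and 91% figures belong to the illustrative record with the lead-in counted as CS.

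A reader might infer that safety or efficacy conclusions are at risk. They are not: response, duration of response and adverse event rates do not use these durations. The effect is confined to descriptive exposure, compliance and RDI summaries, which are worth correcting before programming.

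**What to change.** In SAP Section 8.1:

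1. End total and IS duration on the same date: the last zero or non-zero dose, capped at treatment discontinuation, death or data cut-off. This matches the dose-intensity denominators. Define the treatment discontinuation date used for the cap.
2. Compute IS duration as a sum over IS intervals, as is already done for CS.
3. State whether the 56-day daily lead-in belongs to IS or CS duration, and make the intended-dose rate consistent with that choice.
4. Add a programmed check that total reconciles with IS + CS, listing any remainder, such as a hold between schedules or zero-dose days after the last CS dose.
5. If time actually on drug is wanted, report days with a non-zero dose as a separate variable.

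The cost is a wording change and minor programming. No data collection, dosing rule or efficacy analysis changes.
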